Post Injection Site Evaluation by Investigator ^[17]			X	X	X	X	X	X	X	X	X	X	X	X	X		
Injection Site Pain Assessment ^[18]				X	X	X	X	X	X	X	X	X	X	X	X		
Concomitant medications ^[19]	X	X		X	X	X	X	X	X	X	X	X	X	X	X	X	X
Adverse Events ^[19]			X	X	X	X	X	X	X	X	X	X	X	X	X	X	X

- [1] Informed consent must be obtained prior to patient participation in any protocol-related activities that are not part of routine care.
- [2] A complete review of the subject's past medical history (liver disease), history of prior symptoms or concurrent diseases (including liver disease), past surgeries, and current therapies (medications and non-medications) will be undertaken
- [3] Vital signs including blood pressure, heart rate, respiration rate, and temperature will be measured at each clinic visit.
- [4] Weight only on visits T1 (Pre-Treatment), T2, T6, T10 and EOT/ET
- [5] Symptom-directed physical examination at clinic visits
- [6] A 12-lead ECG will be repeated during the study
- [7] FibroTest (requires fasting for 12 hours or more) combines 5 standard biomarkers (gamma-glutamyltransferase, total bilirubin, alpha-2-macroglobulin, apolipoprotein A1, and haptoglobin). The Acti-Test adds a marker for inflammatory activity (alanine aminotransferase: ALT). These markers are weighted depending on the patient's age and gender.
- [8] Fibroscan or equivalent non-invasive imaging test is acceptable
- [9] Liver MRI will be performed to evaluate MRI-derived biomarkers such as proton density fat fraction (PDFF) and corrected T1 (cT1).
- [10] Hemoglobin, Hematocrit (HCT), Red Blood Cells (RBC), White Blood Cells (WBC) with total and differential count, absolute lymphocyte count, absolute neutrophil count (ANC) and platelets.
- [11] Serum Biochemistry will include:
 - Hepatic function/NASH indicators: Total bilirubin, Direct bilirubin, alkaline phosphatase, aspartate aminotransferase (AST)/SGOT, alanine aminotransferase (ALT)/SGPT, Prothrombin Time (PT), International Normalized Ratio (INR), albumin, total protein, Triglycerides, Cholesterol (Low density lipoprotein), creatine kinase, Gamma-glutamyltransferase (GGT), and serum CK-18
 - Renal function indicators: blood urea nitrogen (BUN), creatinine, eGFR
 - Electrolytes: sodium, potassium, chloride, calcium and bicarbonate

Other: Fasting blood Glucose , Serum HbA1C, Thyroid profile

Note: Screening laboratory testing can be repeated once during the 28-day screening window based on the Investigator's clinical judgement).

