4.4 UNSCHEDULED VISITS

In the event that the subject will return to clinic at a time other than a regularly scheduled study visit, the visit will be regarded as an unscheduled visit. Assessments at unscheduled visits are at the discretion of the Investigator. All pertinent findings, including adverse events or changes in medications, will be noted in the eCRF.

Any hospitalization or ER visits in between the scheduled visits should be promptly notified to the site staff.

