If subjects with abnormal baseline liver indices develop elevations of AST or ALT $>2x$ baseline or Total Bilirubin (TBL) $>1.5x$ baseline values during the study, the tests will be repeated within 48-72 hours. If there are persistent elevations (AST or ALT $>2x$ baseline or TBL >1.5 baseline values) upon repeat testing, then close observation of the subjects per below should be implemented and discontinuation of the study treatment will be considered as per [Section 5.1](#). During the close observation period, liver enzyme and serum bilirubin tests will need to be repeated two or three times weekly. Frequency of retesting can decrease to once a week or less if abnormalities stabilize or the study treatment has been discontinued and the subject is asymptomatic.

Additionally, further gastroenterology or hepatology consultations and/or liver biopsy can be considered per Investigator's discretion.

If patient is unable to come to clinic for blood draw during the close observation period, laboratory testing can be performed locally, and the results should be promptly communicated to the investigator site. A decision to discontinue or temporarily interrupt the study drug will be considered based on factors that include how much higher than baseline the ALT and AST are relative to the upper limit of normal (ULN) and how much the AST and ALT levels have increased relative to baseline, in addition to whether there is a concomitant elevation of bilirubin or INR. The study treatment will be discontinued or temporarily interrupted under the following conditions:

- If Baseline Measurements (BLM) were $<2x$ ULN, The study treatment should be discontinued if ALT or AST increases to $>5x$ BLM
- If BLM was $2x$ ULN but $<5x$ ULN, The study treatment will be discontinued if ALT or AST increases to $3x$ BLM
- If BLM was $5x$ ULN, The study treatment will be discontinued if ALT or AST increases to $>2x$ BLM
- If ALT or AST increases $>2x$ BLM and the increase is accompanied by a concomitant increase in TB to $>2x$ BLM or the INR concomitantly increases by 0.2, The study treatment will be discontinued

- If any subject presents with signs or symptoms of fatigue, nausea, vomiting, right upper quadrant pain or tenderness, fever, rash, and or eosinophilia (>5%), the study treatment should be discontinued

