7.9 CLINICAL LABORATORY ASSESSMENTS

Blood samples will be collected for analysis of the following parameters:

- Hematology (Complete Blood Count) will be performed at SV, T1 (prior to first dose), T2, T6, T10, EOT/ET visits.
- Biochemistry will be performed at SV, T1 (prior to first dose), T2, T6, T10, EOT/ET and FU visits.

Note: Screening laboratory test can be repeated once during the 28-day screening window based on the Investigator's clinical judgement).

- Serum pro-inflammatory biomarkers including IL-1 alpha, IL-1 beta, IL-6, RANTES (CCL5), TNF-alpha, TNF-beta, CRP will be performed at T1 (prior to first dose), T2 (pre-dose), T6 (pre-dose), T10 (pre-dose), EOT/ET and FU visits.
- FibroTest (requires fasting for 12 hours or more) combines 5 standard biomarkers (gamma-glutamyltransferase, total bilirubin, alpha-2-macroglobulin, apolipoprotein A1, and haptoglobin). The Acti-Test adds a marker for inflammatory activity (alanine aminotransferase: ALT). FibroTest will be performed at SV, T1 (prior to first dose), T2, T6, T10, EOT/ET visits.
- Serology tests including HBs Ag, HCV Ab and HCV RNA (only performed if HCV Ab is positive), HIV Ab, Hepatitis A and Hepatitis E Abs will be performed at SV.
- Anti-Drug antibodies (ADA) to PRO 140 at T1 (prior to first dose), T2 (pre-dose), T6 (pre-dose), T10 (pre-dose), EOT/ET and FU visits.
- PK assessment at T1 (prior to first dose), T2 (pre-dose), T6 (pre-dose), T10 (pre-dose), EOT/ET and FU visits.

- Serum pregnancy test (for female subjects of childbearing potential) at SV.
- Monocyte/T cell CCR5 biomarker assay at T1 (prior to first dose), T2 (pre-dose), T6 (pre-dose), T10 (pre-dose), EOT/ET and FU visits.

Note: In case subjects have already completed their EOT/ET and FU visits, site should use the Unscheduled Visit option to collect blood sample for Monocyte/T Cell CCR5 analysis.

Urine samples will be collected for analysis of the following parameters:

- Urine pregnancy at T1 (prior to first dose), T6, T10, EOT/ET visits.

Note: A urine sample will be collected from female subjects of childbearing potential. This test will be performed at the study site using a commercially available kit.

- Urine analysis testing at SV, T1 (prior to first dose), T2, T6, T10, EOT/ET visits.

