Urine samples will be tested for color, appearance, specific gravity, pH, protein, glucose, occult blood, ketones, leukocyte esterases, nitrites, bilirubin, urobilinogen. Microscopic examination of urine sediment will be performed if there are abnormalities in macroscopic urinalysis results. Microscopic urine tests include bacteria, cast, crystals, epithelial cells, RBC and WBC.

All laboratory reports will be reviewed by the Investigator. Abnormal results that are considered by the Investigator to be clinically significant will be recorded as adverse events. In order to make the determination of clinical significance the testing may be needed to be repeated as per Investigator's judgement. Validated, quality-controlled laboratory data will be transferred to the main database for analyses.

Table 7-1: Central Lab Parameters

CBC Parameters	Biochemistry Parameters	Urinalysis
Hemoglobin	Liver Function Tests / NASH Markers	pH
Hematocrit	Total Bilirubin	Appearance
RBC count	Direct Bilirubin	Color
WBC count	Alkaline Phosphatase (ALP)	Specific gravity
WBC Differential	Alanine Aminotransferase (ALT) (or SGPT)	Turbidity
Absolute lymphocyte count	Aspartate Aminotransferase (AST) (or SGOT)	Ketones
Absolute neutrophil count	Prothrombin Time (PT)	Bilirubin
Platelet count	International Normalized Ratio (INR)	Blood
Serology		Glucose
HBs Ag, HCV Ab and HCV RNA (if required), HAV Ab, HEV Ab, HIV Ag	Albumin	Protein
Miscellaneous		Nitrites
Serum pregnancy test	Triglycerides	Urobilinogen
Urine pregnancy test (for female subjects of childbearing potential)	Cholesterol (Low density lipoprotein)	Leukocyte esterases
Anti-Drug Antibodies (ADA) to PRO 140	Creatine kinase	Note: Microscopic examination of urine sediment will be performed if there are abnormalities in macroscopic urinalysis results. Microscopic urine tests include bacteria, cast, crystals, epithelial cells, RBC and WBC.
PK evaluations	Gamma-glutamyltransferase (GGT)	
Monocyte/T cell CCR5 biomarker assay	Serum CK-18	
Pro-inflammatory Biomarkers		
IL-1 alpha, IL-1 beta, IL-6, RANTES (CCL5), TNF-alpha, TNF-beta, CRP	Renal Function Tests blood urea nitrogen (BUN)	
FibroTest		
Gamma-glutamyltransferase* Total bilirubin* Alpha-2-macroglobulin Apolipoprotein A1 Haptoglobin. ALT*	Creatinine eGFR Electrolytes Sodium Potassium Chloride Calcium Bicarbonate Other: Fasting Blood Glucose Serum HbA1c Thyroid profile	
*Part of Liver Function Tests Panel		

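### Section 5.1 stops treatment on an INR rise but does not require INR in the liver-signal repeat or close-observation tests it sets for subjects with abnormal baseline liver indices

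*Protocol*

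**What the plan says.** The drug-induced liver injury text in Protocol section 5.1 works in steps.

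- **Entry.** The follow-up rule covers subjects whose baseline liver indices are abnormal. If AST or ALT exceeds 2x baseline, or total bilirubin exceeds 1.5x baseline, "the tests will be repeated within 48-72 hours". The only tests named in that sentence are AST, ALT and total bilirubin.
- **Close observation.** If the elevation persists, "During the close observation period, liver enzyme and serum bilirubin tests will need to be repeated two or three times weekly". Testing may fall to weekly or less once values stabilise, and may be done at a local laboratory. Discontinuation is to be considered; it is not automatic.
- **Decision factors.** The decision to stop or interrupt takes in "whether there is a concomitant elevation of bilirubin or INR".
- **Stopping conditions.** One bullet combines ALT or AST above 2x BLM with either bilirubin above 2x BLM or an INR change: "the INR concomitantly increases by 0.2, The study treatment will be discontinued".

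INR belongs to the serum biochemistry panel. Footnote 11 of Table 4-2 lists "Prothrombin Time (PT), International Normalized Ratio (INR), albumin, total protein, Triglycerides", and Table 7-1 places INR among the liver function tests. Section 7.9 sets the timing: "Biochemistry will be performed at SV, T1 (prior to first dose), T2, T6, T10, EOT/ET and FU visits". Between those visits, section 4.4 applies: "Assessments at unscheduled visits are at the discretion of the Investigator".

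**The concern.** The combined stopping bullet has two laboratory limbs beside the enzymes: bilirubin and INR. The follow-up testing that section 5.1 requires watches bilirubin but not INR. A site that follows the text exactly can keep dosing a subject under close observation who has already met a stopping condition that the protocol itself chose, because no required test would show it before the next scheduled panel.

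This is a matter of patient safety and of consistency between sites: one that orders INR on its own judgement will apply the rule differently from one that draws only what is listed. Estimation of the MRI-PDFF effect is not at stake.

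**Working it through.** **1. Does any text order INR between scheduled panels?**

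| Place | What it requires | INR required? |
|---|---|---|
| 5.1, repeat at 48-72 h | AST, ALT, total bilirubin | No |
| 5.1, close observation | Liver enzymes (which may include ALP, since inclusion 7b groups it with AST and ALT) and bilirubin | No |
| 5.1, decision factors | Names INR as something to weigh | Not ordered |
| Table 4-2 footnote 11, Table 7-1 | INR is in the biochemistry panel | Only when the panel is drawn |
| 7.9 | Panel on treatment at T2, T6, T10 and EOT/ET | Yes, at those visits |
| 4.4 | Investigator's choice at unscheduled visits | No |

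**2. Spacing of required INR draws.** From Table 4-2: T2 is Day 8, T6 Day 36, T10 Day 64, EOT Day 92.

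- Nominal gaps: 36 - 8 = 28, 64 - 36 = 28, 92 - 64 = 28 days.
- Each gap is four weekly steps of 7 ± 1 days: 4 × 6 = 24 to 4 × 8 = 32 days.
- Doses strictly inside each gap: T3-T5 (Days 15, 22, 29), T7-T9 (Days 43, 50, 57), T11-T13 (Days 71, 78, 85). That is three each time.
- T1 to T2 is only 7 days, and T1 is the pre-dose baseline, so the 28-day spacing applies from T2 on.

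**3. Required draws without a required INR.** After the repeat, 28 - 3 = 25 to 28 - 2 = 26 nominal days remain.

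- At two or three draws a week: 25/7 × 2 = 7.1 to 26/7 × 3 = 11.1, so about 7 to 11 draws.
- If testing drops to weekly: 25/7 = 3.6 to 26/7 = 3.7, so 3 or 4 draws.

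**4. The enzyme range in which the gap exists.** Section 5.1 has separate enzyme-only stops, so INR matters only below them.

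- BLM below 2x ULN: the enzyme stop is above 5x BLM. The gap runs from above 2x up to 5x BLM.
- BLM from 2x to below 5x ULN: the enzyme stop is at 3x BLM. The gap runs from above 2x to below 3x BLM.
- BLM at 5x ULN: the enzyme stop is already above 2x BLM, so there is no gap.

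Illustration with assumed baselines for a man, using the protocol's upper ALT limit of 63 IU/L:

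- BLM 80 (80/63 = 1.27x ULN): ALT above 2 × 80 = 160 and up to 5 × 80 = 400 IU/L.
- BLM 150 (150/63 = 2.38x ULN): ALT above 2 × 150 = 300 and below 3 × 150 = 450 IU/L.

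**5. Size of the INR trigger.** Taking the rise from baseline and assuming a baseline INR of 1.0, the condition is met at 1.0 + 0.2 = 1.2. That is still under the entry limit of 1.3 in inclusion 7e. The entry limit triggers nothing on treatment. The comparison shows only that so small a change has to be measured and set against baseline to be noticed.

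**6. After the change.** The first required INR after the detecting panel would come 2 to 3 days later, with the repeat. At two or three draws a week, later ones would be 7/3 = 2.3 to 7/2 = 3.5 days apart.

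**The case against.** The strongest reply is that a sensible site would measure INR anyway. Section 5.1 tells the investigator to weigh it, it sits in the same panel as ALT and bilirubin, section 4.4 permits it at any unscheduled visit, and the laboratory manual, which is not among the documents, may already put PT/INR in the repeat kit. This stands as far as it goes: the documents do not show that INR would go unmeasured, only that section 5.1 does not require it. It does not remove the point. Weighing a result is not ordering it, and a local laboratory runs what is requested. If the manual covers INR, section 5.1 should say so.

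Four stronger readings might be inferred, and the documents do not support them.

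- **That the gap affects every subject.** Section 5.1 sets repeat and close-observation testing only for those with abnormal baseline liver indices. For others it sets no such draws, so the draw counts above do not describe them.
- **That an absolute stop is being missed.** The INR bullet says treatment will be discontinued, but the lead-in to the bullets also allows temporary interruption, and potential liver injury appears in 5.1 among the reasons for which discontinuation may occur, in consultation with the Medical Monitor. The force is mixed.
- **That 28 days and three doses is the usual exposure.** It is a ceiling. INR is normally known at the detecting panel; bilirubin, enzymes and symptoms remain under watch; and the investigator may stop sooner.
- **That eosinophilia belongs here too.** Section 5.1 lists it as a sign in any subject, without tying it to close observation. Nothing here supports adding a blood count.

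**Conclusion.** The point holds in a limited form and is a cheap improvement. For subjects with abnormal baseline liver indices, section 5.1 contains an INR-based stopping condition that its own required follow-up tests cannot detect.

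The exposed case needs all of the following: an elevation that persists on repeat; ALT or AST above 2x BLM but short of the enzyme-only stop; bilirubin at or below 2x BLM; none of the listed symptoms; dosing continued; and an INR rise that begins after the detecting panel. In that case the worst-case wait for a required INR, counted from the detecting panel, is 28 days (24 to 32 with windows), with three weekly doses in between.

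The documents give no rate for this combination; the number of subjects is probably small. The primary endpoint and the analysis are not affected. The conclusion rests on the protocol text alone and would reduce to a drafting remark if the laboratory manual already requires PT/INR at these draws.

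**What to change.** In section 5.1, name PT/INR in both places where follow-up tests are set: the 48-72 hour repeat and close observation. Suggested wording for the second: *Liver enzymes, total bilirubin and PT/INR are to be measured two or three times a week for as long as close observation lasts, at the site or at a local laboratory, and INR is to be compared with the subject's baseline value.* The note defining BLM should name INR among its examples, so that the 0.2 rise has a stated reference.

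The cost is one or two sentences, one extra analyte and possibly one extra tube at draws already required. No visits are added.

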5.2 SUBJECT REPLACEMENT

Subject replacement is not applicable in this study.

5.3 DATA COLLECTED FROM WITHDRAWN SUBJECTS

Every attempt should be made to collect follow-up information. The reason for withdrawal from the study will be recorded in the source documents and on the appropriate page of the CRF.

Before a subject is identified as lost-to-follow up, the site should make all reasonable efforts to contact the subject. These attempts must be documented and should include at a minimum one phone call and one certified letter.

In the event that a subject is withdrawn from the study at any time due to an adverse event or SAE, the procedures stated in [Sections 9.2](#) and [9.4](#) must be followed.

5.4 SCREEN FAILURES

A subject who signed a consent form, but did not meet the inclusion/exclusion criteria is classified as a screen failure. Subject number, demographics and reason for screen failure will be recorded.

In the event that a subject initially fails to meet inclusion/exclusion criteria and is later reconsidered for participation, will be re-consented and assigned a new screening number at the time of re-screening. Subjects who fail their first screening attempt may be re-screened again (i.e., up to two

screenings) and may be enrolled if they are found to meet all inclusion and no exclusion criteria at the subsequent screening visit.

5.5 CLINICAL TRIAL STOPPING CRITERIA

The clinical trial should be halted if any of the following occurs:

- Three patients develop the same Grade 3 AE attributed to the study drug per CTCAE v5.0
OR
- Two patients develop any Grade 4 AE attributed to study drug per CTCAE v5.0
OR
- One patient develops a grade 5 AE attributed to study drug per CTCAE v5.0

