5.1 SUBJECT WITHDRAWAL

A subject who enters the Treatment Phase but does not complete the study, as defined in this section, is considered to have prematurely withdrawn (early terminated) from the Study.

All subjects have the right to withdraw at any point during treatment without prejudice to future care. It will be documented whether or not each subject completed the clinical study. If for any subject, study treatment or observations were discontinued, the reason(s) will be recorded.

Subjects WILL be withdrawn from the study, in consultation with the Medical Monitor and the Investigator, if any of the following are met:

- A subject is significantly non-compliant with the requirements of the protocol.
- The Investigator determines that it is in the best interest of the subject.
- Subject chooses to withdraw or is withdrawn due to an adverse event
- A subject becomes pregnant

Note: The pregnancy will be followed to term for safety follow-up. Relevant safety information collected after the study has completed will be reported as supplemental information.

- Discontinuation of study by Sponsor
- Subject becomes lost to follow-up (LTf)
- Subject experiences unacceptable toxicity
- Subject voluntarily withdraws from treatment (follow-up permitted)
- Subject withdraws consent (no follow-up permitted)

Discontinuation of study treatment for the individual subject MAY occur if, in consultation with the Medical Monitor and the Investigator, any of the following are met:

- A subject is treated with a prohibited medication.
- Diabetic subjects with an increased HbA1c results of >9% or experiencing significant changes in glucose control requiring modification to the dosage or regimen of antidiabetic medication
- Major protocol violation ([Section 0](#))

- Subjects who have two occurrences of a Grade 2 or higher allergic/hypersensitivity reaction directly related to the study drug that lead to permanent discontinuation of study drug.
- Subjects experiencing grade 3 or higher AE (per CTCAE v5.0) that is possibly or probably related to the study drug OR grade 4 or higher AE regardless of attribution to the study drug.
- Subjects considered to potentially have Drug-Induced Liver Injury (DILI) as described below.

Drug- induced liver Injury (DILI)

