9.2 REPORTING AND FOLLOW-UP OF ADVERSE EVENTS

Report initiation for all AEs and serious adverse events (SAEs), (see [Section 9.3](#)), will begin at the time of the first treatment and continue up to the final study visit. All events will be followed to resolution or until 30 days after the subject completes the study. A final assessment of outcome will be made at that time.

All AEs must be recorded in the subject's medical records and on the CRF. AEs will be reported using customary medical terminology along with the following information: the onset and end dates, whether the event is considered to be a SAE (see [Section 9.3](#)), the impact the event had on study treatment (see [Section 0](#)), the CTCAE grade (intensity) of the event (see [Section 0](#)), the causality of the event (see [Section 0](#)), whether treatment was given as a result of the event (see [Section 0](#)), and the outcome of the event (see [Section 0](#)).

Impact on Study Treatment

The impact the event had on the study treatment will be assessed as either: dose increased, dose not changed, dose reduced, drug interrupted, drug withdrawn, unknown, and not applicable. The "not applicable" assessment will be used only when the subject is no longer in the treatment period of the protocol or died.

CTCAE Grade (Intensity) Assessment

The guidelines outlined in CTCAE v5.0 will be used for assessing the intensity of the event. The general guidelines for assessing the AE grade appear below. Full guidelines may be obtained at https://ctep.cancer.gov/protocolDevelopment/electronic_applications/docs/CTCAE_v5_Quick_Reference_5x7.pdf

Table 9-1: CTCAE v5.0 General Guidelines

Grade	Description
Grade 1	Mild; asymptomatic or mild symptoms; clinical or diagnostic observations only; intervention not indicated.
Grade 2	Moderate; minimal, local or noninvasive intervention indicated; limiting age-appropriate instrumental activities of daily living (ADL)*.
Grade 3	Severe or medically significant but not immediately life-threatening; hospitalization or prolongation of hospitalization indicated; disabling; limiting self care ADL†.
Grade 4	Life-threatening consequences; urgent intervention indicated.
Grade 5	Death related to AE.‡

*Instrumental ADL refer to preparing meals, shopping for groceries or clothes, using the telephone, managing money, etc.

†Self care ADL refer to bathing, dressing and undressing, feeding self, using the toilet, taking medications, and not bedridden.

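### The halting rule in Protocol Section 5.5 is met by three patients with the same attributed Grade 3 event, but read literally it is not met if one of the three is Grade 4

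*Protocol*

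**What the plan says.** Protocol Section 5.5 opens with "The clinical trial should be halted if any of the following occurs" and lists three limbs joined by OR:

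- "Three patients develop the same Grade 3 AE attributed to the study drug per CTCAE v5.0"
- "Two patients develop any Grade 4 AE attributed to study drug per CTCAE v5.0"
- "One patient develops a grade 5 AE attributed to study drug per CTCAE v5.0"

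The Grade 3 and Grade 4 limbs each name one grade, without any extension to higher grades. Nothing elsewhere in the protocol lets a Grade 4 event count towards the Grade 3 tally. The SAP contains no halting rule.

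Table 9-1 (Protocol Section 9.2) fixes the order of severity. Grade 3 is "Severe or medically significant but not immediately life-threatening" and Grade 4 is "Life-threatening consequences; urgent intervention indicated".

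Protocol Section 5.1 lists criteria under which an individual subject may stop treatment. One of them covers "Subjects experiencing grade 3 or higher AE (per CTCAE v5.0) that is possibly or probably related to the study drug", and the same bullet extends to Grade 4 or above whatever the attribution. That criterion counts upwards across grades.

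**The concern.** A toxicity trigger should not become harder to meet as events become more severe. Here it does at one point. Three patients with the same severe, drug-attributed event halt the trial. If one of those three events had been life-threatening instead, the Grade 3 tally would be two (three needed) and the Grade 4 tally one (two needed), and no limb would be met.

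Section 5.5 is the only numerical trial-level toxicity trigger in the documents, and neither document describes a safety committee that would review such a cluster independently. Someone applying the text literally would find no prespecified reason to halt in the worse case.

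**Working it through.** **Inputs.** The three limbs come from Protocol Section 5.5 and the severity order from Table 9-1. Group sizes come from Protocol Section 8.3: 30 subjects per randomised arm and up to 30 in Part 2, so 30 for one leronlimab group and 30 + 30 = 60 for both. The plan gives no operating characteristic for the rule, so there is no figure to reproduce.

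**Rule as written.** Let n3 be the number of patients with the same attributed AE at Grade 3, n4 the number with any attributed Grade 4 AE, and n5 the number with an attributed Grade 5 AE. Each patient is counted at one grade. Halt if n3 ≥ 3, or n4 ≥ 2, or n5 ≥ 1.

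| Grades of the same attributed AE | n3 | n4 | n5 | Limb met | Halt? |
|---|---|---|---|---|---|
| 3, 3, 3 | 3 | 0 | 0 | Grade 3 | Yes |
| 3, 3, 4 | 2 | 1 | 0 | none | **No** |
| 3, 4, 4 | 1 | 2 | 0 | Grade 4 | Yes |
| 4, 4, 4 | 0 | 3 | 0 | Grade 4 | Yes |
| 3, 3, 5 | 2 | 0 | 1 | Grade 5 | Yes |

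**Is this the only reversal?** Every grade pattern of one AE in one to five patients was listed, and each event was raised by one grade in turn. The only step that turns a halt into no halt is 3,3,3 to 3,3,4. With four or more Grade 3 cases, three remain after one worsens. With 3,3,3,4, worsening a Grade 3 case gives two Grade 4 patients. Raising a Grade 4 event gives a Grade 5. For comparison only, a reading in which each limb counts its grade and above was applied to the same patterns. It differs from the literal reading only at 3,3,4.

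**Illustrative size.** The documents give no event rates, so both inputs here are assumptions. Let p be the chance that a subject has the AE at attributed Grade 3 or 4, and q the share of such cases that are Grade 4. Then

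P(end at 3,3,4) = C(n,3) p³ (1−p)^(n−3) × 3q(1−q)².

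At q = 0.2 the second factor is 3 × 0.2 × 0.64 = 0.384. For n = 30 and p = 0.10, the first factor is 4060 × 0.001 × 0.9²⁷ = 0.236, and 0.236 × 0.384 = 0.091. The grid at q = 0.2 is:

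| p | n = 30 | n = 60 |
|---|---|---|
| 1% | 0.1% | 0.7% |
| 2% | 0.7% | 3.3% |
| 3% | 1.9% | 6.3% |
| 5% | 4.9% | 8.8% |
| 10% | 9.1% | 3.2% |
| 15% | 6.5% | 0.4% |

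The chance of exactly three cases peaks at p = 3/n, which is 10% for n = 30 and 5% for n = 60. The values near 9% are therefore maxima over p. At q = 0.1 and q = 0.3 the second factor is 0.243 and 0.441, so the n = 30 maximum becomes 0.236 × 0.243 = 5.7% and 0.236 × 0.441 = 10.4%.

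A separate exact trinomial calculation set the Grade 3 rate at 5% or 10% and the Grade 4 rate at 1% to 5%. It gave 0.5% to 9.3%.

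**The case against.** The strongest reply is that the gap is one pattern and that other controls surround it. Much of that stands.

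- **Stronger reading: dosing must continue until a fourth patient is harmed.** A reader might infer this, but the text does not support it. If one of the two Grade 3 patients worsens to Grade 4, or has any other attributed Grade 4 event, the Grade 4 limb is met. An attributed Grade 5 event in any of the three also meets the rule. Section 5.5 says when the trial should halt, and does not bar a halt in other circumstances.
- **Stronger reading: a halt already triggered is cancelled.** The text says nothing of the kind. The comparison is between two alternative outcomes in three patients.
- **Stronger reading: Sections 5.1 and 5.5 contradict each other.** They do not. Section 5.1 is a discretionary criterion for one subject, and Section 5.5 is a count across the trial. The difference shows that the authors used cumulative wording in one place and not in the other.
- **Other controls.** Individuals may be discontinued under Section 5.1. SAEs are reported within 24 hours (Section 9.4), the sponsor evaluates the drug continuously (Section 9.5.1), and Section 5.1 contemplates the sponsor ending the study. These reduce the consequence, but they rest on discretion, whereas Section 5.5 sets a trigger in advance.
- **A Grade 4 patient may have passed through Grade 3 and so count in the Grade 3 limb.** This is arguable. The protocol does not say whether the tally uses worst grade or every grade reached, so the reading is available but not secured.
- **Event rates may be low.** Section 1.6 reports no related SAEs at 525 mg or 700 mg, in more than 250 and more than 150 subjects respectively. Those are other populations, and a Grade 4 laboratory value need not be an SAE, so this is only indicative. It does point towards the low end of the range.

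**Conclusion.** The point holds as a narrow defect in the wording of a participant-protection rule. On the literal text, 3,3,3 meets the rule and 3,3,4 does not, although the protocol ranks the second as worse. That result follows from the wording alone and needs no assumed rate, provided that each patient is counted at a single grade.

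The practical size is uncertain and often small. With 20% of cases assumed to be Grade 4, it is about 0.1% to 9% over event rates of 1% to 15% (0.1% to 9.1% in 30 subjects, 0.4% to 8.8% in 60). This takes one AE term, independent patients and no other attributed Grade 4 or 5 events. A reader might take 9% as typical, but it is the maximum over the event rate at that Grade 4 share, and nothing in the documents shows that rates lie there.

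**What to change.** The sponsor should reconcile the Grade 3 and Grade 4 limbs of Section 5.5 with each other, noting that Section 5.1 counts upwards across grades for individual subjects. The section should then state two things:

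1. How a Grade 4 occurrence of the same attributed AE counts towards the Grade 3 tally.
2. Whether the tally uses each patient's worst grade or every grade reached.

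The thresholds of three, two and one are not questioned, and no clinical rule is proposed. The choice is the sponsor's. The cost is a few words in a protocol amendment. Depending on that choice, the trial might halt earlier when a cluster mixes Grades 3 and 4. No new data, patients or committee are needed.
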